Protocol 12-202, Phase I study of Lenalidomide plus mitoxantrone, etoposide, and cytarabine for patients with relapsed and refractory AML has just been completed at DF/HCC. Results were presented in abstract form at the American Society of Hematology, December 2015. (54)

The primary objective of this Phase I trial was to evaluate the safety of lenalidomide in combination with MEC for relapsed acute myelogenous leukemia and determine a safe Phase II dose and schedule. The secondary objectives included time to neutrophil (>500) and platelet recovery ($> 20K$), the complete response rate with and without platelet recovery, and the treatment-related mortality within the first 45 days. Patients received lenalidomide in escalating doses at dose levels: 5 mg, 10 mg, 25 mg and 50 mg. Lenalidomide was given initially Days 1-14, and then due to neutropenia was decreased to Days 1-10. The chemotherapy was given as follows: Mitoxantrone $8 \text{ mg/m}^2/\text{day}$ Days 4-8, Etoposide $100 \text{ mg/m}^2/\text{day}$ Days 4-8, and Cytarabine $1000 \text{ mg/m}^2/\text{day}$ Days 4-8. Thirty-six patients were enrolled with a median age of 61 years. Forty-five percent of patients had received 2 or more prior chemotherapy regimens, and 22% had received a prior stem cell transplant. Thirteen patients entered complete remission and one patient had complete remission with incomplete count recovery for a response rate of 39%. The median time to ANC > 500 was 30 days and the median time to platelet recovery $> 20,000$ was 34 days. Two of 6 patients treated with lenalidomide for 14 days had no count recovery at Day 42. After the dose adjust to 10 days, only 1 of 13 patients at lenalidomide 50 mg daily x 10 days had prolonged count recovery. Thus, the recommended phase 2 dose is 50 mg daily for 10 days. There were 4 deaths on study, deemed unrelated to study drug. One patient died of sepsis, one of infection, and two of respiratory failure.

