7.2.3 Attribution

The Investigator must determine the causal relationship between the administration of lenalidomide, the administration of MEC, and the occurrence of an AE/SAE as Not Related or Related as defined below:

Not Related: Means a causal relationship of the adverse event to IP administration is unlikely or remote, or other medications, therapeutic interventions, or underlying conditions provide a sufficient explanation for the observed event.

Related: Means there is a reasonable possibility that the administration of IP caused the adverse event. 'Reasonable possibility' means there is evidence to suggest a causal relationship between the IP and the adverse event.

Causality should be assessed as per the categories below and provided for every AE/SAE based on currently available information. Causality is to be reassessed and provided as additional information becomes available.

- Definite – The AE is *clearly related* to the study treatment.
- Probable – The AE is *likely related* to the study treatment.
- Possible – The AE *may be related* to the study treatment.
- Unlikely – The AE is *doubtfully related* to the study treatment.
- Unrelated – The AE is *clearly NOT related* to the study treatment.

If an event is assessed as possibly, probably or definitely related to a comparator, ancillary or additional IP that has not been manufactured or provided by Celgene, please provide the name of the manufacturer when reporting the event.

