11.2 Treatment-related Mortality

All deaths in the absence of relapse of the primary malignancy will be considered treatment

CONFIDENTIAL

This document is confidential. Do not disclose or use except as authorized.

related mortality. The cumulative incidence of treatment related mortality at 50 days will be measured.

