13.1.1 Evaluation of toxicity

All participants will be evaluable for toxicity from the time of their first treatment up until day 50 or the initiation of other therapy. In the phase I study of 35 patients, 3 dose limiting toxicities were noted due to prolonged count recovery. In the current study, we will monitor for toxicities and assess them as a part of the two stage design described above. If, within the first 10 patients on study, 3 or more experience prolonged neutrophil or platelet recovery beyond day 45 in the absence of disease, or other unacceptable toxicities felt related to the study regimen, we will put the study on hold to investigate further enrollment. The probability of putting the study on hold is 7%, if the true probability of delayed count recovery is 10%.

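### The Section 13.1.1 hold rule does not name death, so a patient who dies before Day 45 without count recovery counts only if the event is judged related to the regimen

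*Combined protocol and SAP*

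**What the plan says.** The hold rule in Section 13.1.1 has two criteria. The first is met if "within the first 10 patients on study, 3 or more experience prolonged neutrophil or platelet recovery beyond day 45 in the absence of disease". The second criterion, which feeds the same count, and the consequence of reaching it are given as "or other unacceptable toxicities felt related to the study regimen, we will put the study on hold". The section gives one operating characteristic: a 7% chance of a hold when the true rate of delayed count recovery is 10%. It does not mention death.

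Three other places bear on how a death would be handled.

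- **Section 7.2.3** calls an event not related if a causal link is improbable, "or other medications, therapeutic interventions, or underlying conditions provide a sufficient explanation for the observed event". It calls an event related if there is a reasonable possibility that treatment caused it.
- **Section 11.2** needs no attribution. It defines treatment-related mortality, measured at 50 days, in a sentence that begins "All deaths in the absence of relapse of the primary malignancy will be considered treatment".
- **Section 2.4.1**, on the phase I study of this combination, reports: "There were 4 deaths on study, deemed unrelated to study drug". On the causes it adds: "One patient died of sepsis, one of infection, and two of respiratory failure".

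**The concern.** The first criterion can be met only by a patient who is alive and followed past Day 45. A patient who dies on, say, Day 25 with counts still low is a non-event for it. That death enters the rule only through the second criterion, which depends on a judgment of relatedness to the regimen. Where the judgment is unrelated, the death adds nothing to the count and also removes a patient who might later have shown delayed recovery. The count then moves the wrong way as fatal toxicity rises.

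The same death could be treatment-related mortality in the final report under Section 11.2 and a non-event for the rule meant to pause enrollment. The trial has no control arm to show an excess of early deaths, and no other rule in the documents sets a numeric limit on them. The two-stage boundaries in Section 13 concern responses only, and the mortality analysis there is descriptive.

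**Working it through.** **Inputs**

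- Rule: 3 or more of 10 patients; delayed recovery at 10% (Section 13.1.1).
- Phase I deaths: 4 (Section 2.4.1), where "Thirty-six patients were enrolled with a median age of 61 years". 4/36 = 11.1%. Section 13.1.1 gives 35 patients; 4/35 = 11.4%, an immaterial difference.
- MEC background death figures (Section 2.2): 1 of 38 (2.6%), 10% and 13%. These come from different studies and are not defined identically.
- A 30% death rate is an assumption, used to show the range.

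**Step 1. The plan's own figure.** With X binomial (10, 0.10):

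P(X ≥ 3) = 1 − (0.3487 + 0.3874 + 0.1937) = 0.0702.

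The stated 7% reproduces. It covers delayed recovery alone.

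**Step 2. No death attributed.** Let d be the probability of death before Day 45 without count recovery, and let delayed recovery be 10% among survivors. The per-patient event probability is p = 0.10(1 − d). At d = 11.1%, p = 0.0889 and

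P(X ≥ 3) = 1 − (0.3942 + 0.3846 + 0.1688) = 0.0524.

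**Step 3. Every early death counted in the same total.** Here p = d + 0.10(1 − d). At d = 11.1%, p = 0.200 and P(X ≥ 3) = 0.322.

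**Step 4. A separate count of deaths alone.** P(3 or more deaths in 10) uses p = d.

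| Death rate d | Existing rule, no death attributed | Existing rule, all deaths attributed | Separate count, 3 or more deaths of 10 |
|---|---|---|---|
| 0 | 7.0% | 7.0% | 0% |
| 2.6% | 6.6% | 11.7% | 0.2% |
| 10% | 5.4% | 29.2% | 7.0% |
| 11.1% | 5.2% | 32.2% | 9.1% |
| 13% | 5.0% | 37.4% | 13.1% |
| 30% (assumed) | 2.8% | 77.9% | 61.7% |

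**Step 5. Partial attribution.** If a share f of early deaths is judged related, p = f·d + 0.10(1 − d). For d = 11.1% and f = 0.5, p = 0.0556 + 0.0889 = 0.1444.

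| Share attributed | Hold probability, d = 11.1% | Hold probability, d = 30% |
|---|---|---|
| 0 | 5.2% | 2.8% |
| 25% | 10.2% | 16.7% |
| 50% | 16.6% | 38.3% |
| 75% | 24.0% | 60.4% |
| 100% | 32.2% | 77.9% |

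**Step 6. Either count triggers.** Treat delayed recovery (a = 0.10) and death (d = 0.111) as mutually exclusive outcomes for each patient. Then

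P(either count ≥ 3) = 1 − Σ 10!/(i! j! (10 − i − j)!) · a^i · d^j · (1 − a − d)^(10 − i − j), summed over i, j = 0, 1, 2.

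This gives 0.158. If the 10% applies to survivors only, as in Step 2, a = 0.0889 and the result is 0.141. Neither figure includes deaths that would also count under the existing relatedness clause.

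**The case against.** The strongest reply is that the rule refers to the study regimen, which includes MEC. Sections 7 and 7.2.3 make the investigator judge relationship to MEC as well as to lenalidomide, and a reasonable possibility is enough for related. An infectious death in aplasia after MEC could well be attributed. With half of early deaths attributed, the existing rule already holds with probability 16.6% at an 11% death rate. With 75% attributed at a 30% rate it holds with probability 60.4%, close to the 61.7% of a separate count. The fall from 7.0% to 5.2% at the phase I rate is also small. All of this stands. It makes the size of the gap depend on attribution but does not close it.

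A reader might infer three stronger things that the documents do not support.

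- **That the four phase I deaths would have gone uncounted here.** They were judged against study drug, not regimen. Section 2.4.1 gives neither their timing nor their disease status, and they pool several lenalidomide doses and two schedules. They show that attribution can exclude deaths, and no more.
- **That early deaths go unwatched.** Section 7.3.5 requires expedited reporting of on-study deaths regardless of causality. Section 7.4.2 sets a 24-hour line for grade 5 events whatever the attribution. The monitoring committee in Section 12.2 may receive summaries of deaths within 30 days of intervention. None of these carries a numeric boundary.
- **That Sections 11.2 and 13.1.1 contradict each other.** An inclusive descriptive endpoint can sit beside an attribution-based trigger, and the early-death-from-toxicity category in Section 11.5 also uses attribution. The two can classify one death differently, which is a gap in monitoring and not an inconsistency of text.

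**Conclusion.** The point holds as a design weakness that should be corrected. Death before Day 45 without count recovery has no route into the hold rule except a judgment of relatedness. To the extent such deaths are judged unrelated, they reduce the chance of a hold: from 7.0% to 5.2% at an 11% death rate and to 2.8% at an assumed 30%. These are the worst case, with no death attributed and 10% delayed recovery among survivors. At a 30% rate the hold probability runs from 2.8% to 77.9% according to the share attributed, so how the rule responds to early deaths cannot be stated in advance. The plan's 7% is correct for delayed recovery alone.

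**What to change.** Add a second, separate count to Section 13.1.1, for example:

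*The study will also be put on hold for review if [number set by the sponsor] or more of the first 10 patients die by Day 50 without relapse, as defined in Section 11.2, regardless of attribution to study treatment. A death with no post-treatment marrow, so that disease status is unknown, counts as an event.*

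The second sentence is needed because Section 10.2 requires a marrow only at count recovery or about Day 35, so disease status may be unknown for an earlier death. The text should also say whether a death with persistent leukemia counts. Section 11.5 defines relapse as reappearance after a documented remission, so Section 11.2 read literally would include such deaths. The assumed death rate should match the choice.

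The sponsor should set the threshold and state its operating characteristics. As an illustration, 3 or more of 10 triggers with probability 9% at an 11% death rate, 13% at 13% and 62% at 30%. It would still miss a 30% rate 38% of the time (100% − 62%) and does not look beyond the tenth patient.

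**Cost.** Deaths to Day 50 are already collected for a secondary objective. The 24-hour line in Section 7.4.2 is footnoted to active participants or 30 days after the last intervention. With lenalidomide ending on Day 10 that is about Day 40, so a phrase extending prompt notice to Day 50 may be needed. The price is more holds at background rates: about 16% for either count at 10% delayed recovery and 11% deaths, against the stated 7%. The existing rule's chance already exceeds 7% when a quarter or more of the deaths are attributed at that rate (10.2% at a quarter, 16.6% at half). A hold is a pause to review enrollment.

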13.1.2 Evaluation of the Primary Efficacy Endpoint

Analyses will be performed on an intent-to-treat basis. Specifically, all eligible participants, except those who are removed and replaced, who are then included in the study, will be assessed for response/outcome to therapy, even if there are major protocol therapy deviations.

APPENDIX A PERFORMANCE STATUS CRITERIA

ECOG Performance Status Scale		Karnofsky Performance Scale	
Grade	Descriptions	Percent	Description
0	Normal activity. Fully active, able to carry on all pre-disease performance without restriction.	100	Normal, no complaints, no evidence of disease.
		90	Able to carry on normal activity; minor signs or symptoms of disease.
1	Symptoms, but ambulatory. Restricted in physically strenuous activity, but ambulatory and able to carry out work of a light or sedentary nature (e.g., light housework, office work).	80	Normal activity with effort; some signs or symptoms of disease.
		70	Cares for self, unable to carry on normal activity or to do active work.
2	In bed <50% of the time. Ambulatory and capable of all self-care, but unable to carry out any work activities. Up and about more than 50% of waking hours.	60	Requires occasional assistance, but is able to care for most of his/her needs.
		50	Requires considerable assistance and frequent medical care.
3	In bed >50% of the time. Capable of only limited self-care, confined to bed or chair more than 50% of waking hours.	40	Disabled, requires special care and assistance.
		30	Severely disabled, hospitalization indicated. Death not imminent.
4	100% bedridden. Completely disabled. Cannot carry on any self-care. Totally confined to bed or chair.	20	Very sick, hospitalization indicated. Death not imminent.
		10	Moribund, fatal processes progressing rapidly.
5	Dead.	0	Dead.

CONFIDENTIAL

This document is confidential. Do not disclose or use except as authorized.

DFCI IRB Protocol #: 16-574

1. INTRODUCTION

The Dana-Farber/Harvard Cancer Center Multi-Center Data and Safety Monitoring Plan (DF/HCC DSMP) outlines the procedures for conducting a DF/HCC Multi-Center research protocol. The DF/HCC DSMP serves as a reference for any sites external to DF/HCC that are participating in a DF/HCC clinical trial.

1.1 Purpose

To establish standards that will ensure that a Dana-Farber/Harvard Cancer Center Multi-Center protocol will comply with Federal Regulations, Health Insurance Portability and Accountability Act (HIPAA) requirements and applicable DF/HCC Standard Operating Procedures.

1.2 Multi-Center Data and Safety Monitoring Plan Definitions

DF/HCC Multi-Center Protocol: A research protocol in which one or more outside institutions are collaborating with Dana-Farber/Harvard Cancer Center where a DF/HCC investigator is the sponsor. DF/HCC includes Dana-Farber/Partners Cancer Care (DF/PCC) Network Clinical Trial Affiliates.

Lead Institution: One of the Dana-Farber/Harvard Cancer Center consortium members (Dana-Farber Cancer Institute (DFCI), Massachusetts General Hospital (MGH), Beth Israel Deaconess Medical Center (BIDMC), Boston Children's Hospital (BCH), Brigham and Women's Hospital (BWH)) responsible for the coordination, development, submission, and approval of a protocol as well as its subsequent amendments per the DFCI IRB and applicable regulatory guidelines (CTEP, Food and Drug Administration (FDA), Office of Biotechnology Activities (OBA) etc.). The Lead Institution is typically the home of the DF/HCC Sponsor. The Lead Institution also typically serves as the Coordinating Center for the DF/HCC Multi-Center Protocol.

DF/HCC Sponsor: The person sponsoring the submitted Multi-Center protocol who takes responsibility for initiation, management and conduct of the protocol at all research locations. In applicable protocols, the DF/HCC Sponsor will serve as the single liaison with any regulatory agencies. The DF/HCC Sponsor has ultimate authority over the protocol and is responsible for the conduct of the study at DF/HCC and all Participating Institutions. In most cases the DF/HCC Sponsor is the same person as the DF/HCC Overall Principal Investigator; however, both roles can be filled by two different people.

Participating Institution: An institution that is outside the DF/HCC and DF/PCC consortium that is collaborating with DF/HCC on a protocol where the sponsor is a DF/HCC Investigator. The Participating Institution acknowledges the DF/HCC Sponsor as having the ultimate authority and responsibility for the overall conduct of the study.

Coordinating Center: The entity that provides administrative support to the DF/HCC Sponsor in order that he/she may fulfill the responsibilities outlined in the protocol

CONFIDENTIAL

This document is confidential. Do not disclose or use except as authorized.

document and DSMP, and as specified in applicable regulatory guidelines. In general, the Lead Institution is the Coordinating Center for the DF/HCC Multi-Center Protocol.

DF/HCC Office of Data Quality (ODQ): A group within DF/HCC responsible ensuring high-quality standards are used for data collection and the ongoing management of clinical trials, auditing, and data and safety monitoring. ODQ also coordinates quality assurance efforts related to multi-center clinical research.

DF/HCC Clinical Trials Research Informatics Office (CTRIO): A group within DF/HCC responsible for providing a comprehensive data management platform for managing clinical trial data.

2. GENERAL ROLES AND RESPONSIBILITIES

For DF/HCC Multi-Center Protocols, the DF/HCC Sponsor, the Coordinating Center, and the Participating Institutions are expected to adhere to the following general responsibilities:

2.1 DF/HCC Sponsor

The DF/HCC Sponsor, [name]., will accept responsibility for all aspects of conducting a DF/HCC Multi-Center protocol which includes but is not limited to:

- Oversee the coordination, development, submission, and approval of the protocol as well as subsequent amendments.
- Ensure that the investigators, study team members, and Participating Institutions are qualified and appropriately resourced to conduct the protocol.
- Include the Multi-Center Data and Safety Monitoring Plan as an appendix to the protocol.
- Ensure all Participating Institutions are using the correct version of the protocol.
- Ensure that each participating investigator and study team member receives adequate protocol training and/or a Site Initiation Visit prior to enrolling participants and throughout trial's conduct as needed.
- Ensure the protocol will be provided to each participating site in a language understandable to all applicable site personnel when English is not the primary language.
- Monitor progress and overall conduct of the study at all Participating Institutions.
- Ensure all DFCI Institutional Review Board (IRB), DF/HCC and other applicable (i.e. CTEP, FDA, OBA) reporting requirements are met.
- Review data and maintain timely submission of data for study analysis.
- Act as the single liaison with the FDA (investigator-held IND trials) as applicable.
- Ensure compliance with all requirements as set forth in the Code of Federal Regulations, applicable DF/HCC requirements, HIPAA requirements, and the approved protocol.
- Commit to the provision that the protocol will not be rewritten or modified by anyone other than the DF/HCC Sponsor.
- Identify and qualify Participating Institutions and obtain accrual commitments prior to extending the protocol to that site.

CONFIDENTIAL

This document is confidential. Do not disclose or use except as authorized.

- Monitor accrual and address Participating Institutions that are not meeting their accrual requirements.

2.2 Coordinating Center

The general responsibilities of the Coordinating Center may include but are not limited to:

- Assist in protocol development.
- Maintain FDA correspondence, as applicable.
- Review registration materials for eligibility and register participants from Participating Institutions in the DF/HCC clinical trial management system (CTMS).
- Distribute protocol and informed consent document updates to Participating Institutions as needed.
- Review and approve Participating Site informed consent forms
- Conduct and document initial and ongoing protocol training
- Oversee the data collection process from Participating Institutions.
- Maintain documentation and cumulative reports of Serious Adverse Event (SAE) reports and Deviations/Violations across all sites and provide to the DF/HCC Sponsor for timely review and submission to the DFCI IRB, as necessary.
- Distribute serious adverse events reported to the DF/HCC Sponsor that fall under the DFCI IRB Adverse Event Reporting Policy to all Participating Institutions.
- Provide Participating Institutions with information regarding DF/HCC requirements that they will be expected to comply with.
- Carry out approved protocol monitoring plan either by on-site or remote monitoring.
- Maintain essential regulatory documents of all Participating Institutions which includes but is not limited to the following: local IRB approvals/notifications from all Participating Institutions, confirmation of Federalwide Assurances (FWAs) for all sites, all SAE submissions, Screening Logs for all sites, IRB approved consents for all sites, and protocol training documentation
- Conduct regular communications with all Participating Institutions (conference calls, emails, etc) and maintain documentation all relevant communications.

2.3 Participating Institution

Each Participating Institution is expected to comply with all applicable federal regulations and DF/HCC requirements, the protocol and HIPAA requirements.

The general responsibilities for each Participating Institution may include but are not limited to:

- Document the delegation of research specific activities to study personnel.
- Commit to the accrual of participants to the protocol.
- Submit protocol and/or amendments to their local IRB.
- Maintain regulatory files as per sponsor requirements.
- Provide the Coordinating Center with regulatory documents or source documents as requested.

CONFIDENTIAL

This document is confidential. Do not disclose or use except as authorized.

- Participate in protocol training prior to enrolling participants and throughout the trial as required (i.e. teleconferences).
- Update Coordinating Center with research staff changes on a timely basis.
- Register participants through the Coordinating Center prior to beginning research related activities.
- Submit Adverse Event (SAE) reports to local IRB per institutional requirements and to the Coordinating Center, in accordance with DF/HCC or other sponsor requirements.
- Submit protocol deviations and violations to local IRB per institutional requirements and to the DF/HCC Sponsor in accordance with DF/HCC requirements.
- Order, store and dispense investigational agents and/or other protocol mandated drugs per federal guidelines and protocol requirements.
- Have office space, office equipment, and internet access that meet HIPAA standards.
- Participate in any quality assurance activities and meet with monitors or auditors at the conclusion of a visit to review findings.
- Promptly provide follow-up and/or corrective action plans for any monitoring queries or audit findings.

